#### 1. OBJECTIVES

## 1.1 Study Design

This is an open-label phase II study of ipilimumab with or without nivolumab for patients with relapsed or refractory (R/R) classic Hodgkin lymphoma (cHL).

Patients who have previously failed a PD-1 mAb will receive 4 cycles of ipilimumab monotherapy and then undergo a restaging PET scan. Patients achieving an objective response will continue ipilimumab maintenance therapy. Patients with SD or progressive disease (PD) (if clinically stable) will receive 4 cycles of combination therapy with ipilimumab and nivolumab followed by ipilimumab maintenance therapy. Patients who have progressive disease after fewer than 4 cycles of ipilimumab are also eligible to proceed to combination therapy with nivolumab and ipilimumab, if they are clinically stable. The primary endpoint will be objective response rate (ORR) to 4 cycles of ipilimumab monotherapy.

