## 1.3 Secondary Objectives

- Best ORR, PRR, CRR assessed by PET/CT (using Lugano criteria and LYRIC criteria) after ipilimumab monotherapy
- Best ORR, PRR, CRR assessed by PET/CT (using Lugano criteria and LYRIC criteria) after ipilimumab and nivolumab combination therapy
- To evaluate the following outcomes among patients receiving ipilimumab maintenance:
  - o DOR and PFS (Lugano criteria and LYRIC criteria)
  - o OS
  - Above endpoints, stratified by best response to PD-1 mAb (non-responder versus responder)
- To evaluate the following outcomes among patients receiving re-induction with ipilimumab/nivolumab combination therapy:
  - o DOR and PFS (Lugano criteria and LYRIC criteria)
  - $\circ$  OS
  - Above endpoints, stratified by best response to PD-1 mAb (non-responder versus responder)
- To evaluate the safety of study treatment (within the entire study popultion, among patients receiving ipilimumab maintenance, and among patients receiving ipilimumab/nivolumab combination treatment) as measured by:
  - o Rate of grade 3 or higher toxicity regardless of attribution
  - o Rate of grade 3 or higher toxicity at least possibly related to study treatment
  - o Rate of grade 2 or higher toxicity at least probably related to study treatment

Protocol version date: v8/06 September 2023

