#### 5. TREATMENT PLAN

## Figure 1 Trial Schema

Patients with R/R cHL who have previously failed a PD-1 mAb will be enrolled. For details regarding dosing, see section 5.1. Study therapy is expected to be administered on an outpatient basis. Patients will receive 4 doses of ipilimumab therapy dosed every 3 weeks (12 weeks), followed by a restaging PET/CT scan. Patients achieving an objective response to ipilimumab monotherapy will receive up to 8 doses of maintenance ipilimumab dosed every 12 weeks (96 weeks), for a total of 108 weeks of study therapy. Patients with SD or PD following ipilimumab monotherapy (who are clinically stable) will receive 4 cycles of combination ipilimumab and nivolumab therapy dosed every 3 weeks (12 weeks), followed by up to 7 doses of maintenance ipilimumab dosed every 12 weeks (84 weeks), for a total of up to 108 weeks of study therapy. Patients who have progressive disease after fewer than 4 cycles of ipilimumab are eligible to proceed to combination therapy with nivolumab and ipilimumab if they are clinically stable. Therapy will be stopped sooner for unacceptable toxicity, patient withdrawal, disease progression, physician decision, or death. Patients achieving a complete response for ≥ 6 months

can elect to stop study therapy.

Patients will be evaluated with PET/CT scans at baseline and again after 4 doses of ipilimumab monotherapy (week 12) (or earlier if there is clinical concern for progression). Among ipilimumab responders, restaging scans will occur prior to ipilimumab maintenance cycle 2 (week 24), cycle 3 (week 36), cycle 5 (week 60), and cycle 7 (week 84). Among ipilimumab non-responders, restaging scans will occur after 4 cycles of ipilimumab + nivolumab combination therapy (week 24) and prior to ipilimumab maintenance cycle 2 (week 36), cycle 4 (week 60), and cycle 6 (week 84). The end-of-treatment assessment will occur 4-12 weeks after the last doses of study therapy (i.e. weeks 112-120 for patients who complete all planned study therapy). Afterwards, patients will be re-imaged every 24 weeks. Patients in CR at any time point may have CT imaging only at subsequent time points.

Toxicity will be continuously monitored and recorded using CTCAE 5 criteria, up to 30 days following the last dose of the study treatment or until resolution of toxicity to grade 1 or baseline, whichever occurs last.

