# Secondary Endpoints

- Best ORR, PRR, CRR assessed by PET/CT (using Lugano criteria and LYRIC criteria) after ipilimumab monotherapy
- Best ORR, PRR, CRR assessed by PET/CT (using Lugano criteria and LYRIC criteria) after ipilimumab and nivolumab combination therapy
- DOR (using Lugano criteria and LYRIC criteria) for patients receiving ipilimumab maintenance
- DOR (using Lugano criteria and LYRIC criteria) for patients receiving ipilimumab and nivolumab combination therapy
- PFS and OS (Lugano criteria and LYRIC criteria)
- Safety
- Above endpoints, stratified by best response to PD-1 mAb (non-responder versus responder)

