# 13.4 Analysis of Secondary Endpoints

Secondary endpoints include, response assessments including ORR (defined as partial response and complete response), the duration of response (DOR) among patients who have achieved a PR or CR (defined as the time from first response to progression or last follow-up), progression free survival (PFS) (defined as the time from treatment start to progression, death or last follow-up, whichever comes first), and overall survival (OS) (defined as time from treatment start to death or last follow-up). The safety of study will be assessed as measured by: the rate of grade 3 or higher toxicity regardless of attribution, the rate of grade 3 or higher toxicity at least possibly related to study treatment, and the rate of grade 2 or higher toxicity at least probably related to study treatment.

For patients who respond to treatment (complete or partial response), duration of response will be calculated from the date of response to the date of progression of disease. Patients still responding at date of last follow-up will be censored. PFS will be calculated as the time from start of treatment to the date of progression, death or last follow-up. OS will be calculated as the time from the start of treatment to the date of death or last follow-up. OS, PFS and DOR will be calculated using Kaplan-Meier methodology. 95% confidence intervals will be calculated for all secondary endpoints.

Correlative studies analyzing tissue samples using MIF and/or MIBI and circulating tumor DNA using next-generation sequencing based platforms are exploratory in nature. This testing is not powered to detect associations, but rather is designed to generate hypothesis for future studies. Completion of correlative studies will depend upon sample collection and budget considerations.

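### Cohort PFS and OS for re-induction and maintenance have no origin of their own, so under 13.4 as written the progression that qualifies a patient for re-induction counts as that cohort's PFS event

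*Combined protocol and SAP*

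**What the plan says.** Section 1.3 sets two secondary objectives on groups formed after baseline: "To evaluate the following outcomes among patients receiving ipilimumab maintenance" and "To evaluate the following outcomes among patients receiving re-induction with ipilimumab/nivolumab combination therapy". Each lists DOR, PFS by both criteria, and OS. Because re-induced patients go on to maintenance, the maintenance group holds two kinds of patient.

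Entry to re-induction is by SD or progression on ipilimumab alone. Section 1.1: "Patients with SD or progressive disease (PD) (if clinically stable) will receive 4 cycles of combination therapy with ipilimumab and nivolumab". Section 5 adds an early route: "Patients who have progressive disease after fewer than 4 cycles of ipilimumab are eligible to proceed to combination therapy", if clinically stable.

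The time origins are study-wide:

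- Section 13.4: "PFS will be calculated as the time from start of treatment to the date of progression, death or last follow-up". OS also runs from start of treatment.
- Section 11.1.2: PFS and OS run from randomization (or registration).
- Section 13.1 gives DOR by cohort ("DOR (using Lugano criteria and LYRIC criteria) for patients receiving ipilimumab maintenance", with a matching line for the combination) but lists PFS and OS on one line with no cohort.

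No section sets an origin at the first re-induction or first maintenance dose, defines a landmark, or says how the qualifying progression is handled. Section 13.3 calls the re-induction analysis descriptive.

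**The concern.** A time-to-event curve for a cohort should start when the patient joins it. Here the only stated clocks start about 12 weeks or more before most patients join, and one way of joining is to have had the PFS event already.

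Two opposite distortions follow. For patients entering re-induction with PD, the PFS event precedes the treatment being described. SD entrants to re-induction and all maintenance entrants are instead credited with time in which they could not have had the event and still been in the cohort. The re-induction Lugano curve would then partly report how many patients progressed on ipilimumab alone. A reader of the published median could not separate the two effects.

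**Working it through.** **What the plan's own figures cover.** The documents give no figure for cohort PFS or OS. The stated design figures do reproduce: with 13 patients and rejection at 4 or more responses, the exact binomial tail is 0.0342 at ORR 10% (stated 0.034) and 0.831 at ORR 40% (stated 0.83). Neither depends on the PFS origin.

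**Guaranteed time, from the schedule in section 5.** Induction is 4 doses every 3 weeks, with restaging at week 12.

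- SD entrant to re-induction: progression-free to about week 12 by definition.
- Monotherapy responder entering maintenance: about 12 weeks, for both PFS and OS.
- Re-induced patient entering maintenance: alive for at least 3c + 12 weeks after c monotherapy cycles, so 15, 18, 21 or 24 weeks for c = 1, 2, 3 or 4. Such a patient may already have a PFS event.

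**Number of early events.** Expected non-responders are 13 × 0.60 = 7.8 at ORR 40% and 13 × 0.90 = 11.7 at ORR 10%. Assume all are clinically stable and enter re-induction. At 30%, 40% or 50% Lugano PD, the events dated before the first combination dose are 2.3, 3.1 or 3.9 of 7.8, and 3.5, 4.7 or 5.9 of 11.7.

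**Effect on the re-induction median (illustration).** Assumptions, none of them from the documents: exponential PFS from the first combination dose with median m, the same for SD and PD entrants; continuous assessment; a share f entering with Lugano PD, all with the event by week 12. With the clock at start of study treatment,

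S(t) = (1 − f) × 2^(−(t − 12)/m) for t > 12,

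so the reported median is 12 + m × log2((1 − f)/0.5) when f < 0.5, and about 12 weeks or less otherwise.

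| f | m (weeks) | Reported median (weeks) |
|---|---|---|
| 0% | 52 | 12 + 52 × 1.000 = 64.0 |
| 30% | 52 | 12 + 52 × 0.485 = 37.2 |
| 40% | 52 | 12 + 52 × 0.263 = 25.7 |
| 50% or more | 52 | about 12 or less |
| 40% | 26 | 18.8 |
| 40% | 104 | 39.4 |

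With the clock at the first combination dose and the qualifying PD not counted, the answer is m in every row. Early crossover does not change the table, because those events also fall by week 12.

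**LYRIC.** If a share r of the PD entrants is classed as indeterminate and then behaves like SD entrants, f becomes f × (1 − r). At f = 40% and m = 52, r = 50% gives 12 + 52 × log2(0.8/0.5) = 47.3 weeks, and r = 100% gives 64.0.

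**Maintenance, monotherapy responders.** The reported median is m + 12: 26, 52 or 104 weeks become 38, 64 or 116 (+46%, +23%, +12%).

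**The case against.** The strongest reply is that *start of treatment* can mean the cohort's own treatment. Section 1.3 defines each cohort by the treatment received, and 13.4 writes *study treatment* for toxicity but plain *treatment* for PFS and OS. The tie between treatment start and baseline measurements in 11.1.1 concerns the reference for DOR and stable disease, not the PFS origin. This reading is open, and it removes the guaranteed time. It does not settle the rest: 13.4 would still not say that the qualifying progression is not an event.

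The figures are also softer than they look. If PD entrants had a 26-week median and SD entrants 52, the cohort's true median at 40% PD would be about 39 weeks, so the gap to 26 shrinks. Assessed only at the scheduled scans (weeks 24, 36, 60 and 84), the three medians would be about 84, 60 and 36 weeks rather than 64, 37 and 26. Both points stand; the direction does not change.

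Some stronger readings should not be drawn:

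- *That the nadir rule makes any unchanged lesion PD at the first combination scan.* In Appendix C the nadir comparison belongs to the CT branch; the PET-CT branch compares uptake with baseline and looks for new foci. A node growing from 2.0 to 2.5 cm also sits on the size boundary between the 0.5 cm and 1.0 cm growth requirements, and Appendix C does not say which measurement decides.
- *That a reported median of 12 weeks or less has a known probability.* With 8 patients and PD shares of 30%, 40%, 50% and 60%, the chance that at least 4 enter with PD is 19%, 41%, 64% and 83%. If the Kaplan-Meier curve must fall below 0.5 (at least 5), it is 6%, 17%, 36% and 59%.
- *That 13.1 contradicts 1.3.* It is only less specific.
- *That the synergy rationale fails.* Section 2.4 rests it on objective responses to the combination, not on cohort PFS.

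**Conclusion.** The gap is real and worth closing before analysis. Applied as written to cohorts formed after baseline, 13.4 puts the PFS event of every Lugano-PD entrant before the first combination dose. It also credits SD entrants with about 12 progression-free weeks, and maintenance entrants with about 12 weeks, or about 15 to 24 weeks of survival after re-induction. The alternative reading of *start of treatment* repairs only the second part.

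That much follows from the entry rules and definitions alone. How far the reported median moves rests on an unknown PD share and on the modelling assumptions above, so the 64, 37 and 26 weeks are illustrations, not predictions.

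A reader might infer that the trial's main conclusion is at risk. It is not: the primary ORR test and the DOR origin are untouched, re-induction is descriptive, and no decision rule uses cohort PFS or OS. The disagreement between 11.1.2 and 13.4 is also small in time: section 4.3 asks external sites to start therapy within 5 days of registration, though 4.1 sets no limit for DF/HCC sites.

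**What to change.** Add to 13.4:

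- Re-induction cohort PFS and OS start at the first ipilimumab + nivolumab dose. Maintenance cohort PFS and OS start at the first maintenance dose, reported separately for monotherapy responders and re-induced patients.
- Progression before that dose is not an event in the cohort analysis.
- For the cohort analysis only, the last scan before that dose is the reference for later progression, with any nadir taken from that scan onward. State whether the 12-week window for LYRIC IR1 restarts there.

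Keep whole-population PFS and OS from a single origin, reconcile 11.1.2 with 13.4, and align the 13.1 list with the cohorts in 1.3.

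A smaller reporting point: 1.3 also asks for toxicity rates "among patients receiving ipilimumab maintenance, and among patients receiving ipilimumab/nivolumab combination treatment". If these are windowed, state both a start (first dose of the phase) and an end (first dose of the next phase, or the end of the protocol's AE collection period). A start alone would let re-induction rates absorb maintenance events.

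Cost: a few sentences and a little more analysis work. Some progression dates must be re-derived against the new reference scan through the central imaging core (11.1.3). The scans are already scheduled at week 12, or earlier on suspected progression, and at week 24, so no visit, scan or sample is added and treatment does not change.

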# 13.5 Reporting and Exclusions

## 13.5.1 Evaluation of Toxicity

All participants who receive at least one dose of study therapy will be evaluable for toxicity from the time of their first treatment.

# 13.5.2 Evaluation of the Primary Efficacy Endpoint

The primary analysis will be performed on all evaluable patients.

## 14. PUBLICATION PLAN

The results of this study will be submitted for presentation at national meetings and for publication in appropriate journals within 24 months of the completion of the study. The first analysis and submission will be conducted when all patients have reached the End of Study visit (or been taken off study).

# APPENDIX A PERFORMANCE STATUS CRITERIA

ECC	OG Performance Status Scale	Karnofsky Performance Scale			
Grade	Descriptions	Percent	Description		
0	Normal activity. Fully active, able to carry on all pre-disease	100	Normal, no complaints, no evidence of disease.		
U	performance without restriction.	90	Able to carry on normal activity; minor signs or symptoms of disease.		
1	Symptoms, but ambulatory. Restricted in physically strenuous activity, but ambulatory and able to	80	Normal activity with effort; some signs or symptoms of disease.		
1	carry out work of a light or sedentary nature ( e.g. , light housework, office work).	70	Cares for self, unable to carry on normal activity or to do active work.		
	In bed <50% of the time. Ambulatory and capable of all self-	60	Requires occasional assistance, but is able to care for most of his/her needs.		
2	care, but unable to carry out any work activities. Up and about more than 50% of waking hours.	50	Requires considerable assistance and frequent medical care.		
3	In bed >50% of the time. Capable of only limited self-care, confined	40	Disabled, requires special care and assistance.		
3	to bed or chair more than 50% of waking hours.	30	Severely disabled, hospitalization indicated. Death not imminent.		
	100% bedridden. Completely disabled. Cannot carry on any self-	20	Very sick, hospitalization indicated.  Death not imminent.		
4	care. Totally confined to bed or chair.	10	Moribund, fatal processes progressing rapidly.		
5	Dead.	0	Dead.		

# APPENDIX B DANA-FARBER/HARVARD CANCER CENTER MULTI-CENTER DATA SAFETY MONITORING PLAN

#### INTRODUCTION

The Dana-Farber/Harvard Cancer Center Multi-Center Data and Safety Monitoring Plan (DF/HCC DSMP) outlines the procedures for conducting a DF/HCC Multi-Center research protocol. The DF/HCC DSMP serves as a reference for any sites external to DF/HCC that are participating in a DF/HCC clinical trial.

# 1.1 Purpose

To establish standards that will ensure that a Dana-Farber/Harvard Cancer Center Multi-Center protocol will comply with Federal Regulations, Health Insurance Portability and Accountability Act (HIPAA) requirements and applicable DF/HCC Standard Operating Procedures.

# 2 GENERAL ROLES AND RESPONSIBILITIES

For DF/HCC Multi-Center Protocols, the following general responsibilities apply, in addition to those outlined in DF/HCC Policies for Sponsor-Investigators:

#### 2.1 External Site

An External Site is an institution that is outside the DF/HCC and DF/PCC consortium that is collaborating with DF/HCC on a protocol where the sponsor is a DF/HCC investigator. The External Site acknowledges the DF/HCC Sponsor as having the ultimate authority and responsibility for the overall conduct of the study.

Each External Site is expected to comply with all applicable DF/HCC requirements stated within this Data and Safety Monitoring Plan and/or the protocol document.

The general responsibilities for each External Site may include but are not limited to:

- Document the delegation of research specific activities to study personnel.
- Commit to the accrual of participants to the protocol.
- Submit protocol and/or amendments to their local IRB. For studies under a single IRB, the Coordinating Center with regulatory documents or source documents as requested.
- Maintain regulatory files as per ICH GCP and federal requirements.
- Provide the Coordinating Center with regulatory documents or source documents as requested.
- Participate in protocol training prior to enrolling participants and throughout the trial as required.
- Update Coordinating Center with research staff changes on a timely basis.
- Register participants through the Coordinating Center prior to beginning research related activities when required by the sponsor.

- Submit Serious Adverse Event (SAE) reports to the Sponsor, Coordinating Center, and IRB of Record as applicable.
- Submit protocol deviations and violations to sponsor, Coordinating Center, and IRB of record as applicable, in accordance with DF/HCC requirements.
- Order, store and dispense investigational agents and/or other protocol mandated drugs per federal guidelines and protocol requirements.
- Participate in any quality assurance activities and meet with monitors or auditors at the conclusion of a visit to review findings.
- Promptly provide follow-up and/or corrective action plans for any monitoring queries or audit findings.
- Notify the sponsor immediately of any regulatory authority inspection of this protocol at the External Site.

# 3 DF/HCC REQUIREMENTS FOR MULTI-CENTER PROTOCOLS

Certain DF/HCC Policy requirements apply to External Sites participating in DF/HCC research. The following section will clarify DF/HCC requirements and further detail the expectations for participating in a DF/HCC Multi-Center protocol.

## 3.1 Protocol Revisions and Closures

The External Sites will receive notification of protocol revisions and closures from the Coordinating Center. When under a separate IRB, it is the individual External Site's responsibility to notify its IRB of these revisions.

- **Protocol revisions:** External Sites will receive written notification of protocol revisions from the Coordinating Center. All protocol revisions must be IRB approved and implemented within a timely manner from receipt of the notification.
- **Protocol closures and temporary holds:** External Sites will receive notification of protocol closures and temporary holds from the Coordinating Center. Closures and holds will be effective immediately. In addition, the Coordinating Center, will update the Participating Institutions on an ongoing basis about protocol accrual data so that they will be aware of imminent protocol closures.

# 3.2 Informed Consent Requirements

The DF/HCC approved informed consent document will serve as a template for the informed consent for External Sites. The External Site consent form must follow the consent template as closely as possible and should adhere to specifications outlined in the DF/HCC Guidance Document on Model Consent Language for Investigator-Sponsored Multi-Center Trials. This document will be provided separately to each External Site upon request.

External Sites are to send their version of the informed consent document to the Coordinating Center for review and approval prior to submission to their local IRB. The approved consent

form must also be submitted to the Coordinating Center after approval by the local IRB for all consent versions.

The Principal Investigator (PI) at each External Site will identify the physician members of the study team who will be obtaining consent and signing the consent form for therapeutic protocols. External Sites must follow the DF/HCC requirement that for all interventional drug, biologic, or device research, only attending physicians may obtain initial informed consent and any reconsent that requires a full revised consent form.

